2.1 Background

2.1.1 Description of Drug Substance (Active Pharmaceutical Ingredient)

QR-010 Drug Substance (DS) is a white to off-white lyophilized powder. It is an anhydrous sodium salt with molecular formula $C_{347}H_{420}N_{122}Na_{32}O_{195}P_{32}S_{32}$ and molecular mass of 12172.66 Daltons. QR-010 DS is stable at ambient temperature but undergoes some degradation when exposed to 80°C and significant degradation when exposed to oxidative stress (0.3% H₂O₂ solution).

2.1.2 Description of Drug Product

2.1.2.1 Drug Product

QR-010 Drug Product (DP) is a solution for nebulization presented in a Type I glass vial containing a clear, colorless solution available at a concentration of 50 mg/mL (2 mL/vial) in 0.7% sodium chloride solution. The DP has a pH between 6.0 and 8.0, and osmolality equal to 0.9% sodium chloride solution. QR-010 DP is labeled with the appropriate information as specified in the clinical protocol and as necessitated by local regulatory requirements. Throughout the document the name used for the DP is: QR-010 Solution for Nebulization.

The eFlow® Nebulizer System [REDACTED] will be used for study drug administration in the European Union (EU). The Investigational eFlow® Nebulizer System [REDACTED] will be used for study drug administration in North America. These devices are identical and will be referred to as eFlow in this protocol.

2.1.2.2 Placebo

Placebo, QR-010 Placebo Solution for Nebulization, is a solution of 0.9% sodium chloride. It is similar to QR-010 Solution for Nebulization except the active ingredient, QR-010, is excluded. The placebo is labeled with the appropriate information as specified in the clinical protocol and as necessitated by local regulatory requirements.

2.1.3 Nonclinical

The nonclinical pharmacology program investigated QR-010 using both in vitro (human cell line and primary cells) and in vivo (mice, Cynomolgus monkeys) systems. The nonclinical pharmacodynamics data demonstrated the inhalation of QR-010 in mice and supported the proposed mechanism of action of treatment with QR-010 in facilitating the phenotypic reversion of $\Delta F508$ CFTR activity to [REDACTED] CFTR activity. These studies are summarized in QR-010 Investigator's Brochure, Section 5.2 - Nonclinical Pharmacology.

Three preliminary studies contributed bio-distribution data for QR-010. These analyses were conducted in mouse variant C57BL/6J (considered wild-type [WT] for the purposes of these studies). One additional 28-day, repeat-dose GLP-compliant toxicity study in Cynomolgus monkeys provided toxicokinetic (TK) data. These studies are summarized in QR-010 Investigator's Brochure, Section 5.3 - Pharmacokinetics and Product Metabolism in Animals.

The nonclinical toxicology program for QR-010 was conducted in accordance with the following guidelines:

- ICH M3 (R2): *Guidance on Nonclinical Safety Studies for the Conduct of Human Clinical Trials and Marketing Authorization for Pharmaceuticals*
- ICH S4 Guidance: *Duration of Chronic Toxicity Testing in Animals (Rodent and Non Rodent Toxicity Testing)*
- ICH S3A Guidance: *The Assessment of Systemic Exposure in Toxicity Studies*

A total of seven toxicity studies in mice and Cynomolgus monkeys contributed relevant data for the determination of safety and maximum recommended starting dose. These studies are summarized in QR-010 Investigator's Brochure, Section 5.4 – Toxicology.

2.1.4 Clinical Experience

No clinical studies have been conducted with QR-010 Solution for Nebulization.

2.2 Study Rationale

A patient with a CF phenotype has a CFTR gene mutation on *both* alleles and may be homozygous for a single mutation or compound heterozygous with a different mutation on each allele. There are nearly 2000 CFTR gene variants. However, only 159 variants have an allele frequency $\geq 0.01\%$ and 127 of those 159 variants meet both the clinical (sweat chloride test) and functional (affects RNA quality/quantity or CFTR protein) criteria to cause CF. Together, these 159 variants account for 96.4% of identified cystic fibrosis alleles. The $\Delta F508$ mutation is the most common allelic mutation and accounts for about 66-70% of identified mutated alleles in northern European and North American populations. According to the Cystic Fibrosis Foundation National Patient Registry Annual Data Report (2012), a total of 23,053 CF patients (86.7% of the CF population in the US) in the US had one or two copies of the $\Delta F508$ mutation (O'Sullivan & Freedman, 2009; Sosnay, *et al.*, 2013).

The $\Delta F508$ mutation (hetero- or homozygous) is a Class II CFTR functional mutation that is characterized by defective CFTR processing; the gene is transcribed but the translated protein product is not trafficked through the endoplasmic reticulum and is degraded before reaching the cell surface. The $\Delta F508$ mutation results in a CFTR protein that is mis-folded, which results in ubiquitination and degradation. As a result, little, if any, CFTR reaches the plasma membrane. The absence of functional CFTR at the apical membrane of ciliated airway epithelial cells of the respiratory tract results in loss of CFTR-mediated ion regulation, which ultimately results in airway inflammation, obstruction, and persistent bacterial infections (Collawn *et al.*, 2012; O'Sullivan & Freedman, 2009). It is the same loss of CFTR-mediated ion regulation that leads to dysfunction in other organ systems, including the gastrointestinal (eg, malabsorption), biliary, pancreatic and sweat exocrine, reproductive (congenital bilateral absence of the vas deferens in males) systems.

Although many organ systems are affected in CF, the most common cause of death is respiratory failure due to progressive loss of lung function and/or pulmonary disease (Davies *et al.*, 2007). Hence, patients with CF would greatly benefit from a therapy targeted to the respiratory system that facilitated the phenotypic reversion of $\Delta F508$ CFTR activity to [REDACTED] normal CFTR activity. Worldwide, there is no marketed therapy that facilitates repair of the CFTR protein by targeting the RNA transcription product of the CFTR gene.

QR-010 is a single-stranded RNA oligonucleotide that is complementary to the CFTR region on the RNA transcription product of the CFTR gene. Hence, QR-010 has the potential to treat all CF patients with the $\Delta F508$ mutation on at least one allele. The QR-010 nonclinical program demonstrated that QR-010 facilitated the phenotypic reversion of $\Delta F508$ CFTR activity to [REDACTED] CFTR activity both in mice that were homozygous for the $\Delta F508$ mutation and in cystic fibrosis human cell cultures with the $\Delta F508$ mutation. The QR-010 nonclinical program also demonstrated the inhalation safety and toxicology of QR-010 in WT mice and WT Cynomolgus monkeys. The clinical development program will investigate the long-term safety and efficacy of QR-010 in treating in adult and pediatric patients who exhibit CF phenotypes with varying degrees of disease severity.

The initial clinical study, PQ-010-001, will be a single- and multiple-ascending dose (SAD and MAD, respectively) study that will evaluate safety, tolerability, and the maximum tolerated dose (MTD) of QR-010 Solution for Nebulization in CF patients who are homozygous for the $\Delta F508$ mutation. Exploratory efficacy endpoints are proposed but the study will not be sufficiently powered to test efficacy. Subjects will have baseline lung function defined as $FEV_1 \geq 70\%$ predicted for safety reasons. The Phase 1b study will be conducted in North America and select European countries.

2.2.1 Dose Selection Rationale

Dose selection was based on the human equivalence dose (HED) and maximum recommended starting dose (MRSD) that were derived from 28-day toxicology studies in mouse and *Cynomolgus* monkey studies, and further details can be found in the Investigator Brochure.

The doses in the intended dose escalation scheme (6.25, 12.5, 25, and 50 mg) in Study PQ-010-001 correspond to the fill dose (mg loaded into the nebulizer) for the nebulizer. The maximum fill volume of the eFlow, the device that will be used to deliver study medication, is 4 mL. In Study PQ-010-001, the fill volume will be 4 mL for all doses in the dose escalation scheme. The doses will be adjusted by diluting the 50 mg/mL solution. The actual delivered dose of QR-010 Solution for Nebulization using the eFlow with a 4 mL fill is $< 80\%$ of the fill dose. Hence, the maximum amount of drug delivered to patients will be approximately 5, 10, 20, and 40 mg under the dose escalation scheme.

The maximum loaded (50 mg) and estimated maximum delivered doses (40 mg) roughly correspond to one-half of the MRSD of 104 mg. In addition, the MRSD incorporated a safety factor of greater than 5 times the pulmonary deposited dose (PDD) (based on data from the 28-day toxicity study that was conducted in *Cynomolgus* monkeys), and it is expected that there will be a lower bioavailability of QR-010 in the lungs of CF patients. In consideration of all the points above, the proposed dose escalation scheme for PQ-010-001 is considered highly conservative.

3.0 STUDY OBJECTIVES

3.1 Primary Objective

The primary objective of the study is to evaluate the safety and tolerability of QR-010 administered by inhalation to subjects with homozygous $\Delta F508$ cystic fibrosis, and to identify the maximum tolerated dose (MTD) of QR-010.

3.2 Secondary Objective(s)

The secondary objectives of the study are:

- To evaluate the change from baseline analysis for laboratory and vital signs
- To evaluate the pharmacokinetics (PK) of QR-010 administered by inhalation.

3.3 Exploratory Objective(s)

An additional objective of the study is to explore the clinical efficacy of QR-010 administered via inhalation by FEV₁, Cystic Fibrosis Questionnaire-Revised (CFQ-R) Respiratory Symptom Score (RSS), change in body weight, and iontophoretic pilocarpine sweat chloride.

4.0 STUDY OVERVIEW

4.1 Criteria for Evaluation

4.1.1 Primary Endpoint

- Incidence and severity of adverse events (AEs) from baseline through end of study
- Occurrence of dose-limiting toxicities (DLT) in each dose cohort from baseline through end of study

4.1.2 Secondary Endpoint(s)

Safety: Changes from baseline to end of treatment or presence of abnormalities on frequent monitoring in laboratory parameters (chemistry, hematology, sputum microbiology, and urinalysis), vital signs, ECG, spirometry, and physical examinations. A chest radiograph will be obtained at screening and at end of treatment (MAD cohorts).

Pharmacokinetics: The PK of QR-010 will be examined in all stages of the study, from first dose through end of study. Specifically, subjects will provide blood, urine and expectorated sputum samples for PK assessments.

4.1.3 Exploratory Efficacy Endpoints

Exploratory efficacy endpoints of clinical activity will include FEV₁, the patient reported outcome measure CFQ-R Respiratory Symptom Score (CFQ-R RSS), body weight, and pilocarpine iontophoresis sweat chloride at the end of study compared to baseline, for MAD cohorts.

The study will not be sufficiently powered to determine efficacy of QR-010 in the treatment of CF. However, changes in clinical outcome measures that are associated with CF will be monitored over the course of the study in all MAD cohorts. Observed changes in these well-established measures of CF health may inform design of future studies, and include FEV₁, body weight, change in CFQ-R RSS, and pilocarpine iontophoresis sweat chloride. Data indicating potential immunogenicity of QR-010 and change from baseline in inflammatory biomarkers will also be captured.

4.2 Study Design

The study is a multicenter, randomized, double-blind, and placebo-controlled Phase 1b SAD and MAD design. The subject, investigator, and site personnel (except pharmacist) will be blinded to treatment, while the sponsor will be unblinded. Sponsor personnel will be unblinded to subject

treatments in order to permit real-time interpretation of the safety, pharmacokinetic, and pharmacodynamic data. The site monitor will remain blinded to individual subject treatment allocation until all monitoring of study data has been completed. To minimize the potential for bias, individual subject treatment randomization information will not be released to the investigator or blinded study site personnel until the study database has been locked.

Eligible subjects with homozygous $\Delta F508$ CF will be randomized at a 3:1 ratio to receive either QR-010 or placebo via oral inhalation (nebulization). This study will be conducted in North America and select European countries.

[figure not shown]
The study includes 2 stages. The first stage is a single ascending dose-escalation (SAD) design to determine safety and tolerability of a single dose of QR-010. The second stage is a multiple ascending dose escalation (MAD) design to further assess the safety, tolerability, and exploratory efficacy of 12 doses of QR-010 over 4 weeks. All doses will be administered in a clinical setting.

For the SAD cohorts, subjects will receive the dose in an inpatient observation unit and be observed for a total 4 days, and will be discharged on Day 4. Subjects will return for PK and safety follow-up as an outpatient on Day 8 (End of Study Visit).

For the MAD cohorts, subjects will receive doses 1 through 12 in a clinic while under observation. On Day 1 and Day 3 subjects will be observed until 12 hours post dose. Following the last dose (dose 12), subjects will return twice for PK sampling, and will be evaluated 7 and 28 days after the last visit for this additional safety monitoring and sampling for PK.

A schematic of the study design is presented in Figure 3.

Figure 3: PQ-010-001 Study Schematic

Single Ascending Dose Escalation Cohorts: The first two subjects of each cohort may be dosed on the same day, at least 4 hours apart. If no significant AEs occur, the remainder of the cohort may be dosed at least 24 hours later, with at least 1 hour between subjects.

After each single dose cohort, an independent Data Safety Monitoring Committee (DSMC) will review available safety data, including 7 days of follow up after administration of QR-010. Dose escalation may occur upon recommendation of the DSMC.

Multiple Ascending Dose Escalation Cohorts: The safety results from the single dose escalation portion of the study will support the initiation of the corresponding multiple dose escalation cohorts, as illustrated in [Figure 3](#).

After each multiple dose cohort, the DSMC will review available safety data, including 7 days of follow up after administration of the last dose of QR-010 (End of Treatment Visit). Dose escalation may occur upon recommendation of the DSMC.

Both Stages: Subjects must sign informed consent before any study-related procedures are initiated. Subjects will receive QR-010 by inhalation via the eFlow device.

Blood, urine and sputum samples will be obtained from all subjects to obtain PK data pre- and post-dosing.

Subjects will undergo clinical and laboratory assessments for safety. Subjects will be withdrawn from the study when intolerable toxicity occurs, or when the subject withdraws consent.

The schedule of assessments is summarized in Appendix 1 and 2.

AE profiles by cohort and dose escalation decisions by the DSMC are communicated to all study sites after DSMC review of cumulative and cohort-specific safety data.

4.3 Dose Escalation

The single dose escalation scheme will test fill doses of 6.25 mg to 50 mg over 4 dose levels, and the multiple dose escalation scheme will test fill doses of 6.25 mg to 50 mg given thrice weekly (tiw) for 4 weeks ([Table 1](#)). As described in Section 2.2.1, the dose delivered to subjects via the eFlow device is < 80% of the fill dose, hence the delivered doses that correspond to the dose escalation schemes are shown in [Table 1](#).

Table 1: Dose Escalation

| Dose Cohort | Fill Dose (mg) | Estimated Exposure Dose < 80% of Fill Dose (mg) |
|-----------------------------------------------------------------|----------------|----------------------------------------------------|
| Single Dose Cohorts | | |
| 1 | 6.25 | 5 |
| 2 | 12.5 | 10 |
| 3 | 25 | 20 |
| 4 | 50 | 40 |
| Multiple Dose Cohorts (administered tiw for 4 Weeks) | | |
| 5 | 6.25 | 5 |
| 6 | 12.5 | 10 |
| 7 | 25 | 20 |
| 8 | 50 | 40 |

tiw = thrice weekly (three times per week)

Dose escalation will initially proceed in single subject cohorts from fill dose level 1 (6.25 mg) to fill dose level 4 (50 mg).

Initiation of MAD Cohort 5 will be based on the safety profile of SAD Cohort 2. Initiation of Cohort 6 will be based on the safety profiles of Cohorts 3 and 5. Similarly, initiation of Cohort 7 will be based on the safety profiles of Cohorts 4 and 6, and finally, the initiation of Cohort 8 will be based on the safety profile of Cohort 7. The first dose between subjects in each cohort must be separated by a minimum of 4 hours.

For the single dose cohorts 1 to 4, dose escalation to the next cohort may occur upon recommendation of the DSMC after the subjects have been observed for at least 7 days and no DLTs have occurred or, if a DLT has occurred, per the dose escalation rules in Section 4.5. For the multiple dose cohorts 5 to 8, dose escalation to the next cohort may occur upon recommendation of the DSMC after the subjects have been observed for at least 7 days after the last dose (End of Treatment Visit). If a DLT occurs in any cohort, the AEs and DLTs will be reviewed by the Investigator and the DSMC before dosing can continue in that cohort. In addition, if ≥ 2 subjects experience a decrease in absolute FEV₁ of $\geq 15\%$ from baseline in any cohort, the data will be reviewed by the DSMC before dose escalation can continue.

The AEs of Interest listed in Table 2 are AEs commonly seen with inhaled products. If AEs of interest occur at a Grade 2 level or higher in a single subject in a cohort, then an additional 4 subjects will be added to the cohort. Any of the Grade ≥ 2 toxicities shown in Table 2, as well as

any other respiratory AEs reported, will be evaluated and considered when making dose escalation decisions. If no additional subjects experience any Grade ≥ 2 AEs of Interest, dose escalation may proceed (if recommended by the DSMC).

The Investigator will base decisions to de-escalate to a lower dose, hold the dose (delay or skip), or discontinue study drug for an individual subject using the CTCAE (modified for CF) toxicity grades, in consultation and agreement with the Sponsor’s Medical Monitor. In addition to the CTCAE (modified for CF) toxicity grades, the Investigator should also review the stopping rules in Section 5.5.3 with regard to decreases in FEV₁.

For the multiple dose cohorts, subjects who experience a DLT (defined in Section 4.4) should be discontinued from study drug (whether or not the event resolves), and the End of Treatment Visit procedures should be conducted. An End of Study Visit should also be conducted 28 days after the last study drug dose.

Table 2: Adverse Events of Interest

| Adverse Event of Interest | Symptoms (Grade ≥ 2 per CTCAE or as Specified Below) |
|--------------------------------------|------------------------------------------------------------------------------------------------------------------------------------------|
| Atelectasis | Symptomatic (eg, dyspnea, cough); medical intervention indicated (eg, chest physiotherapy, suctioning); bronchoscopic suctioning |
| Hypotension | non-urgent medical intervention indicated |
| Bronchospasm | symptomatic, medical intervention indicated |
| Liver Function Test Elevation | alanine aminotransferase (ALT) > 3-5 x ULN or aspartate aminotransferase (AST) > 3-5 x ULN AND a doubling from the baseline value |
| Pneumonitis | Symptomatic; medical intervention indicated; limiting instrumental ADL |
| Crackles | Scattered or focal |
| Dyspnoea | Shortness of breath with minimal exertion; limiting instrumental ADL |
| Hypoxia | Decreased oxygen saturation with exercise (eg, pulse oximeter < 88%); intermittent supplemental oxygen |

ADL = Activities of Daily Living

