4.5 Determination of Maximum Tolerated Dose (MTD)

The MTD is defined as one dose level below the dose level at which 2 subjects receiving QR-010 experience a dose limiting toxicity (DLT) for dose cohorts 1-4 or within the first 4 weeks for dose cohorts 5-8. Dose escalation will occur based on the number of DLTs encountered according to the rules in Table 3, as assessed by the DSMC. Dose escalation will continue until the MTD is reached or the maximum dose included in the study, whichever is lower. With the highest planned fill dose of 50 mg, subject exposure will be approximately < 40 mg (< 80% efficiency of the eFlow including residual volume). For the MTD determination, the fill dose will be used.

Table 3: Dose Escalation Rules

| Number of Subjects Receiving QR-010 With a DLT at a Given Dose | Dose-Escalation Decision Rule |
|-----------------------------------------------------------------------|-------------------------------------------------------------------------------------------------------------------------------------------------------------------------------------------------------------------------------------------------------------------------------------------------------------------------------------------------------------------------------------------------------------------------------------------------------------------------------------------------------------------|
| 0 of 6 | Proceed to next dose level |
| 1 of 6 | If one serious AE (SAE) or Grade \geq 2 AE occurs, four additional subjects will be enrolled at the same dose. If no additional subjects experience a similar SAE or Grade \geq 2 AE in the same organ class, the dose escalation may continue pending review of safety by the DSMC. If \geq 2 subjects experience similar SAE or Grade \geq 2 AE of the same organ class, dose escalation is to be stopped, pending review by the DSMC. The preceding dose may be considered the MTD by the DSMC. |
| \geq 2 of 6 | Dose escalation will be stopped. The preceding dose will be considered the MTD. |

DLT = dose-limiting toxicity; MTD = maximum tolerated dose (one dose level lower than the dose level at which 2 or more subjects experience a DLT of the same organ class)

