5.2 Selection of Subjects

Screening of subjects will be performed within 14 days prior to dosing. Medical history, physical examination and vital signs will be recorded. Subjects will undergo electrocardiogram (ECG), chest Xray (CXR), spirometry, and clinical laboratory safety testing. During the study subjects will be permitted to continue on their chronic medications that are considered standard of care for CF. For subjects using inhaled anti-infective agents, preferably the same therapy and dose should be administered throughout the study period (Refer to Section 6.3.1). Subjects with signs of a pulmonary exacerbation or other acute illness will not be included.

The exact number of subjects needed to complete the study depends on the number of cohorts required to reach the MTD and the number enrolled in each dose-escalation cohort. The number of subjects for each of the single dose and multiple dose escalation cohorts is 8 subjects, for a total of 64 subjects, but could theoretically expand to approximately 96 subjects if there are DLTs that require every dose cohort to be expanded. Subjects will be enrolled at approximately 20 study sites in North America and select European countries.

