13.2 Determination of Sample Size

This is a Phase 1 safety study designed to evaluate the safety, tolerability and PK of QR-010. The sample size is not based on power calculations. It is chosen based on clinical experience and considered to be adequate to fulfill the objectives of the study.

Approximately 64 subjects will be enrolled in the study, with 8 subjects per cohort (6 QR-010 and 2 placebo), 32 each in the SAD and MAD portions of the study. The exact number of subjects enrolled is dependent on whether any dose level are to be expanded due to the occurrence of DLTs.

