## **4. STATISTICAL METHODS**

### **4.1. Sample Size Justification**

This is a Phase 1 safety study designed to evaluate the safety, tolerability and PK of QR-010. The sample size is not based on power calculations. It is chosen based on clinical experience and considered to be adequate to fulfill the objectives of the study.

Approximately 64 subjects will be enrolled in the study, with 8 subjects per cohort (6 QR-010 and 2 placebo), 32 each in the SAD and MAD portions of the study. The exact number of subjects enrolled is dependent on whether any dose levels are to be expanded due to the occurrence of AEs of interest.

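### Protocol 4.3 and Table 3 give different triggers for expanding a cohort, and no passage says how the two fit together

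*Protocol*

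**What the plan says.** **Trigger in Protocol 4.3.** "If AEs of interest occur at a Grade 2 level or higher in a single subject in a cohort, then an additional 4 subjects" are added. The sentence does not limit the event to QR-010 recipients, to DLTs or to events judged related. Escalation may then go ahead, if the DSMC recommends it, provided no additional subject has any Grade 2 or higher AE of interest.

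**Trigger in Protocol 4.5, Table 3 (SAP 2.3, Table 2).** The rows are indexed by "Number of Subjects Receiving QR-010 With a DLT at a Given Dose". At 0 of 6 the instruction is "Proceed to next dose level". Expansion appears only in the 1-of-6 row. The text of that row acts on one serious AE (SAE) or Grade 2 or higher AE, after which "four additional subjects will be enrolled at the same dose". Escalation may continue if no added subject has a similar event in the same organ class.

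**DLT definition (Protocol 4.4).** A DLT is an allergic reaction or acute bronchospasm that needs medical intervention, or another acute AE of interest that needs it immediately.

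**Stated cause of expansion.** Protocol 13.2 calls the final number "dependent on whether any dose level are to be expanded due to the occurrence of DLTs". The synopsis says the same, and Protocol 5.2 reaches about 96 subjects "if there are DLTs that require every dose cohort to be expanded". SAP 4.1 otherwise follows 13.2 but reads "dependent on whether any dose levels are to be expanded due to the occurrence of AEs of interest".

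**The concern.** An escalation rule in a first-in-human trial should give one answer for one set of data. Here a cohort with one Grade 2 AE of interest and no DLT is told to enrol four more subjects by one section and to move to the next dose by another. Under the literal wording of 4.3, an event in a placebo subject is enough to trigger expansion.

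At stake are when cohorts expand, how many subjects are likely to be enrolled, and how soon the next dose opens. The MTD is affected only at one remove: it is defined by DLTs in QR-010 subjects, but the number of subjects treated at a dose changes the chance of observing a second DLT there.

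**Working it through.** **The plan's own figures.** 8 cohorts × 8 subjects = 64, and 8 × (8 + 4) = 96. Both match Protocol 5.2. There is no power calculation to reproduce.

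**The two rules side by side.**

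| Question | Protocol 4.3 | Protocol Table 3 |
|---|---|---|
| Triggering event | Grade ≥2 AE of interest | Row entered on one DLT; its text acts on an SAE or any Grade ≥2 AE |
| Subjects counted | Any in the cohort | QR-010 recipients |
| Subjects added | 4 | 4 |
| AE of interest, no DLT | Expand | Proceed |
| Test after expansion | No further Grade ≥2 AE of interest of any kind | No similar SAE or Grade ≥2 AE in the same organ class |

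**Can the conflicting state occur?** Yes. Protocol Table 2 lists hypotension managed without urgency, crackles with no intervention criterion, and transaminase elevation. Each can be a Grade 2 or higher AE of interest without meeting Protocol 4.4.

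**After expansion.** Suppose the first event is a bronchospasm DLT in a QR-010 subject, so both rules expand, and an added subject then has Grade 2 hypotension. The 4.3 condition fails, while the Table 3 condition is met. The row labels stop at 6. If the 3:1 ratio in Protocol 13.3.1 also applies to the four added subjects, which neither section states, an expanded cohort has 6 + 3 = 9 QR-010 subjects.

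**How often the rules differ.** The documents give no event rates, so these inputs are assumptions:
- p is the chance that a subject has a Grade 2 or higher AE of interest. It is the same in both arms and independent between subjects.
- f is the share of those events that are DLTs. Allergic reactions, which are DLTs but not in Protocol Table 2, are left out.
- A single subject is read as at least one.

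Section 4.3 expands with probability 1 − (1 − p)^8. Table 3 is at 0 of 6 with probability (1 − pf)^6. The rules differ when some subject among the 8 has an event but none of the 6 on QR-010 has a DLT: (1 − pf)^6 − (1 − p)^8.

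| p | f = 0 | f = 1/2 | f = 1 (placebo-only events) |
|---|---|---|---|
| 3% | 1 − 0.7837 = 22% | 0.9133 − 0.7837 = 13% | 0.8330 − 0.7837 = 5% |
| 5% | 1 − 0.6634 = 34% | 0.8591 − 0.6634 = 20% | 0.7351 − 0.6634 = 7% |
| 10% | 1 − 0.4305 = 57% | 0.7351 − 0.4305 = 30% | 0.5314 − 0.4305 = 10% |

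The f = 0 column is also the share of all cohorts that 4.3 expands, whatever f is. If a single subject means exactly one, that share is 8p(1 − p)^7 = 19%, 28% or 38%.

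**Expected sample size**, if all eight cohorts run and each expands at most once:
- Under 4.3: 64 + 32 × (0.216, 0.337, 0.570) = 71, 75 and 82.
- Under the 1-of-6 row with f = 1/2 and q = p/2: 64 + 32 × 6q(1 − q)^5 = 64 + 32 × (0.083, 0.132, 0.232) = 67, 68 and 71.

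**Test after expansion.** The chance that at least one of four added subjects has a further AE of interest is 1 − (1 − p)^4 = 11%, 19% or 34%. How often that event would also be similar and in the same organ class cannot be computed from the documents.

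**The case against.** The strongest reply is that 4.3 is an extra gate placed in front of Table 3. Escalation is never automatic: Protocol 4.2, 4.3 and 4.5 all put it in the hands of the DSMC. Section 4.3 already adds one gate outside Table 3, the DSMC review when two or more subjects lose at least 15% of FEV1. SAP 2.5.2 also sends Grade 2 or higher AEs of interest promptly to an unblinded DSMC. This stands in part. A reader might infer that a cohort is obliged to expand and escalate at once. The documents do not support that, because 0 of 6 DLTs never forces escalation. But no passage describes 4.3 as a gate on top of Table 3, and the layered reading would not remove the different tests after expansion or the statements that tie expansion to DLTs alone.

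A second reply is that Table 3 is not purely a DLT rule, because the 1-of-6 text acts on an SAE or Grade 2 or higher AE. That is correct, and it shows that Table 3 disagrees with its own column heading. It does not bring Table 3 into line with 4.3.

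A third is that Table 3 does cover expanded cohorts. A reader might infer that it has no rule for them, but the 1-of-6 row contains one. What is missing is the count that applies to the larger cohort. Since the MTD is defined by a number of subjects and not a proportion, that is mainly a labelling gap.

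SAP 2.5.1 also refers to the DSMC charter for the DLT and MTD criteria. The charter was not supplied and may settle practice, but it would not make the protocol text consistent.

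**Conclusion.** The inconsistency is real and lies in the wording, not in a design choice. For a cohort with a Grade 2 or higher AE of interest and no DLT, 4.3 and Table 3 point in different directions, and no passage says which prevails or that both apply. Table 3 is inconsistent within itself, the tests after expansion differ, and the protocol and SAP name different causes of expansion.

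The size depends on assumed rates. With 3%, 5% or 10% of subjects affected, the rules differ in about 13%, 20% or 30% of cohorts if half of the events are DLTs. The extremes are 22%, 34% or 57% if none are, and 5%, 7% or 10% if all are. The first extreme is the worst case, since bronchospasm that needs intervention can be both an AE of interest and a DLT.

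A reader might infer that the MTD or the sample size is wrong. Neither follows. A placebo event, or an AE of interest that is not a DLT, does not count towards the MTD definition, and 64 and 96 hold under either trigger.

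**What to change.** Reconcile the synopsis (number of subjects), Protocol 4.3, 4.5 with Table 3, 5.2 and 13.2, and SAP 2.3 with its Table 2 and SAP 4.1, into one expansion rule. It should state:
- which event triggers expansion;
- whether events in one arm or both count;
- the criterion for escalating after expansion;
- the allocation of the four added subjects and the count that applies to an expanded cohort;
- whether 4.3 is an additional condition on Table 3 or is replaced by it.

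The 1-of-6 row should use the same event in its label and its text. Check the DSMC charter against the result. This review does not say which rule is right.

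The cost is a protocol amendment with ethics approval, matching SAP wording and, if needed, charter wording. No planned figure changes. For cohorts already decided, the study report should record which rule was applied.
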